9.3 Adverse Events Reporting Timeline

Life-threatening or fatal unexpected adverse events associated with the use of the study drug or procedures must be reported to the IRB within 24 hours of discovery of the incident with subsequent follow-up submission of a detailed written report.

The FDA will be notified by telephone or facsimile transmission of a human adverse event that is fatal or life-threatening no later than 7 calendar days after receiving the respective human adverse event information, followed by the subsequent submission of a written IND Safety Report.

Serious and unexpected adverse events associated with the use of the study drug or procedures will be reported to the IRB with subsequent follow-up submission of a detailed written report in accordance with the respective policies and procedures of the IRB. Written IND Safety Reports will be submitted to the FDA as soon as possible and, in no event, later than 15 calendar days following the investigator-sponsor's receipt of the respective adverse event information.

A summary report of the findings will be prepared and submitted to the regulatory agencies.

9.4 Expected Adverse Events

The following information is obtained from the package insert for tranexamic acid.

Tranexamic acid should be reduced in patients with renal insufficiency because of the risk of accumulation. Ureteral obstruction due to clot formation in patients with upper urinary tract bleeding has been reported in patients treated with tranexamic acid injection (for this reason patients with visible hematuria will be excluded from the study population). Thromboembolic events (e.g., deep vein thrombosis, pulmonary embolism, cerebral thrombosis, acute renal cortical necrosis, and central retinal artery and vein obstruction) have been rarely reported in patients receiving tranexamic acid. Patients with a previous history of thromboembolic disease may be at increased risk for venous or arterial thrombosis. An orthopedic meta-analysis demonstrated no higher risk of venous thromboembolism following hip and knee replacement, surgeries typically thought to be at increased risk of thromboembolism [27]. These findings were supported by a surgical meta-analysis, which found the risk of thromboembolic events with tranexamic acid was uncertain but the risk ratio of events was not increased overall [28]. The CRASH-2 trial utilizing tranexamic acid also found no differences in death from vascular occlusive events [21]. In this study, tranexamic acid will not be administered

concomitantly with Factor IX Complex concentrates or Anti-inhibitor Coagulant concentrates, as the risk of thrombosis may be increased.

Tranexamic acid may cause dizziness and therefore may influence the ability to drive or use machines. Convulsions have also been reported, particularly in patients receiving tranexamic acid during cardiovascular surgery and in patients inadvertently given tranexamic acid into the neuroaxial system.

Focal areas of retinal degeneration have developed in cats, dogs, and rats following oral or intravenous tranexamic acid at doses between 250 to 1600 mg/kg/day (6 to 40 times the recommended usual human dose) from 6 days to 1 year. The incidence of such lesions has varied from 25% to 100% of animals treated and was dose-related. At lower doses, some lesions have appeared to be reversible. Limited data in cats and rabbits showed retinal changes in some animals with doses as low as 126 mg/kg/day (only about 3 times the recommended human dose) administered for several days to two weeks. No retinal changes have been reported or noted in eye examinations in patients treated with tranexamic acid for weeks to months in clinical trials. Tranexamic acid should be discontinued if changes in examination results are found.

An increased incidence of leukemia in male mice receiving tranexamic acid at doses equivalent to as high as 5 g/kg/day may have been related to treatment. Hyperplasia of the biliary tract and cholangioma and adenocarcinoma of the intrahepatic biliary system have been reported in one strain of rats after dietary administration of doses exceeding the maximum tolerated dose for 22 months. Hyperplastic, but not neoplastic, lesions were reported at lower doses. Subsequent long-term dietary administration studies in a different strain of rat, each with an exposure level equal to the maximum level employed in the earlier experiment, have failed to show such hyperplastic / neoplastic changes in the liver. No mutagenic activity has been demonstrated in several in vitro and in vivo test systems.

Gastrointestinal disturbances (nausea, vomiting, diarrhea) may occur but disappear when the dosage is reduced. Allergic dermatitis, giddiness, and hypotension have been reported occasionally. Hypotension has been observed when intravenous injection is too rapid. A rare but important potential adverse effect is anaphylactic shock.

9.4.1 Drug Interactions: Avoid Concomitant Use

Avoid concomitant use of Tranexamic Acid with any of the following: Anti-inhibitor Coagulant Complex (Human); Estrogen Derivatives (Contraceptive); Progestins (Contraceptive)

9.4.2 Drug Interactions: Increased/Decreased Effect/Toxicity

Tranexamic Acid may increase the levels/effects of: Anti-inhibitor Coagulant Complex (Human)

The levels/effects of Tranexamic Acid may be increased by: Estrogen Derivatives (Contraceptive); Progestins (Contraceptive); Tretinoin (Systemic)

The levels/effects of Tranexamic Acid may be decreased by: There are no known significant interactions involving a decrease in effect.

10. Loss To Follow-Up

10.1 Death

Due to the severity of underlying disease it is possible that patients may die due to progression of their disease or complications of their treatment prior to completion of treatment with the study drug. It is estimated that fewer than 5% of study patients will die prior to determination of primary and secondary endpoints. In the event that a participant dies prior to completion of the study, data will be included up to the time of their death. Death will be recorded on the end of study form. Additional information to be documented will include the time from consent and attribution of cause of death (due to thrombosis, due to bleeding or due to other causes).

10.2 Study Withdrawal

Subjects are free to stop the study drug at any time. If a patient withdraws their consent for further participation, the subject will be asked to grant consent for the study team to passively monitor their outcomes for major clinical events. For each patient at the end of therapy, the date and time that the study drug is voluntarily stopped will be recorded, along with the reason that the subject so elected. An End of Study form will document whether the subject is:

- Stopping study drug, but will continue to follow all other study-defined procedures and monitoring
- Stopping study drug and study-defined procedures and monitoring but allows investigators to passively monitor their medical record and follow-up for vital status up to 30 days after their last dose of study drug.
- Discontinuing all further contact with study investigators

In order to avoid any doubt, if subjects withdraw consent it will be explained to them that any data obtained up to the point of consent withdrawal will be included in study analysis, regardless of their consent for future monitoring.

The patient's physician or the principal investigator may withdraw the patient from the study for any reason.

10.3 Hospital Discharge

Patients discharged from the hospital within 30 days of activation of the study drug will receive their assigned study drug up until the day of discharge. The day of discharge will be the final day of therapy with the study drug. They will be contacted at 7 days (+/- 3 days) and 30 days (+/- 3 days) post cessation of the study drug. These visits may take place in the outpatient clinic (if coinciding with a regularly scheduled return appointment) or by telephone. During these visits patients will be asked for any bleeding or thrombotic events since study drug cessation.

11. Statistical Considerations and Analysis

11.1 Statistical Hypothesis

The hypothesis is that tranexamic acid can be safely added to standard care regimens in patients with hematologic malignancies or solid tumors during periods of severe thrombocytopenia and that the study dose of tranexamic acid will sufficiently suppress fibrinolysis

11.1.1 Primary Endpoints

- Assessment of feasibility of recruitment by monitoring number of patients screened, number of patients eligible for enrollment and rate of recruitment (both start-up and ongoing) during study period
- Assessment of safety of tranexamic acid in this population by reported adverse events, serious adverse events and death.
- Assessment of the suppression of fibrinolysis by tranexamic acid will consider the difference in fibrinolytic activity in blood samples obtained from participants at the start of the study prior to receipt of the study drug and after achieving steady state.

11.1.2 Secondary Endpoints

- Assessment of the effect of tranexamic acid on bleeding will consider the difference in the proportion of patients experiencing WHO Grade 2 or higher bleeding between the two study arms following activation of the study drug and until study drug cessation, the proportion of patients with any grade bleeding event following activation of study drug, the highest grade of bleeding experienced during study period and the length of time from study drug activation to WHO Grade 2 or higher bleeding event
- Assessment of the effect of tranexamic acid on platelet transfusion requirement will consider the difference in the number of platelet transfusions administered per patient between the study arms following activation of the study drug and until study drug cessation.

11.2 Randomization

Patients will be randomized by the investigational pharmacy staff to receipt of either tranexamic acid or placebo (normal saline) in a 1:1 fashion. Randomization will be further balanced within blocks of size four. Patients will not be stratified by disease group owing to the small sample size.

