5.2 Randomization

This trial is designed as a prospective, randomized, controlled, blinded (patient, caregiver, physician, assessor) trial with two parallel groups and a primary endpoint of feasibility and safety. Randomization will be performed as block randomization with a 1:1 allocation within blocks of size four.

When a consented participant's platelet count falls to $\leq 50,000/\mu\text{L}$ and the platelet count is expected to continue to fall and remain $\leq 20,000/\mu\text{L}$ for 5 days or longer, the patient will be randomized to either the tranexamic acid arm or the placebo arm by the investigational pharmacy. When the randomized subject's platelet count is $\leq 30,000/\mu\text{L}$ with an expectation that the platelet count will be $\leq 20,000/\mu\text{L}$ for 5 days or longer the study drug will be activated. Activation of the study drug will act as time point zero for all study endpoints.

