5.3 Enrollment Period

Screening will continue until the target population is achieved (20 activated subjects total). The enrollment period will extend over 18 months. The expected enrollment is estimated to be 14 randomized subjects per year. Both arms will have a target enrollment of 10 activated subjects

6. Interventions

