6.2 Concomitant Care

Patients enrolled on trial must have a prophylactic platelet transfusion threshold of $\leq 10,000/\mu\text{L}$ (for patients with solid tumors or hematologic malignancies not undergoing BMT) or $\leq 20,000/\mu\text{L}$ (for patients undergoing BMT) at the time of randomization. Prophylactic platelet transfusions will be given when morning platelet count is below the above values for prophylactic transfusions. Therapeutic platelet transfusions above these thresholds will be allowed at the discretion of their treating physician (for cases including active bleeding, for an expected platelet count of $\leq 10,000$ or $\leq 20,000/\mu\text{L}$ the following morning, planned invasive procedures with the need for an increased platelet threshold or trauma). Clinicians will be allowed to exercise discretion to transfuse platelets for any reason should they feel there is a clinical reason to do so. In cases where a platelet transfusion is given for invasive procedures or trauma the subject will return to the study platelet transfusion threshold following this event when determined safe to do so by the treating physician. If, following enrollment and study drug activation, the subject subsequently has an event which leads to the need for a platelet transfusion threshold of greater than the study protocol, they will remain on study.

Type and dose of platelet transfusion will not be specified. If a patient appears to develop platelet refractoriness (which is defined as two sequential transfusions with a repeat platelet count after a 4hour period of $\leq 5000/\mu\text{L}$) then clinicians may exercise their judgement as to use of matched platelets or alloantibody testing. Data on type of platelet transfusion administered will be collected. For any platelet transfusions given

above the study threshold the rationale will be recorded on the daily transfusion assessment form.

Patients will receive red blood cell transfusions as per the standard care of their treating physician.

No other medication changes are directed in this protocol and standard care will otherwise be followed.

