11.5 Statistical Analysis Planned

All statistical comparisons will be based on a two-sided model using a 0.05 level of significance and two-sided 95% confidence intervals.

Data on the number of patients screened, the number of patients eligible for study inclusion, the number of eligible patients who consent to study inclusion and the number of consented patients activated to the study drug will be organized in CONSORT diagram. Run chart may also be used to demonstrate study momentum over time period of study enrollment in graphical form. Suppression of fibrinolysis will be analyzed by matched pair analysis using a T-test of means.

For secondary endpoints, events of WHO Grade 2 or higher bleeding will be compared through the use of odds ratio or T-test statistic of means. The mean number of platelet transfusions will be analyzed using a T-test statistic of means.

Patients will be followed for all clinical outcomes regardless of adherence to the prescribed regimen for the study drug.

Additional statistical analysis will be considered at the time of trial completion based on the data obtained.

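### Platelet transfusions are compared by an unadjusted t-test, although BMT and non-BMT patients have different transfusion triggers and BMT status is known at enrollment

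*Combined protocol and SAP*

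**What the plan says.** Section 11.5 gives the analysis: "The mean number of platelet transfusions will be analyzed using a T-test statistic of means". It names no covariate, no stratified analysis and no breakdown by BMT. It adds only that further analyses may be considered at trial completion in light of the data.

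Section 6.2 sets the prophylactic trigger by group. It is 10,000/µL or lower "for patients with solid tumors or hematologic malignancies not undergoing BMT" and 20,000/µL or lower for patients undergoing BMT. Prophylactic platelets follow when the morning count is below the group's value.

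On allocation, section 5.2 says "Randomization will be performed as block randomization with a 1:1 allocation within blocks of size four", and section 11.2 adds "Patients will not be stratified by disease group owing to the small sample size". No other section balances BMT. Section 8.1 records current treatment at enrollment, including BMT source and donor details.

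The endpoint (section 11.1.2) is the number of platelet transfusions per patient from activation to study drug cessation. It is secondary.

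**The concern.** The protocol links the transfusion trigger to BMT status, so BMT status can be expected to affect the transfusion count whichever arm a patient is in. With 10 patients per arm and no balancing, one arm can easily receive several more BMT patients. Part of the observed difference in transfusions would then reflect case mix, and the planned analysis has no step that separates the two. Even when the arms are balanced, the BMT versus non-BMT difference remains in the error term and widens the interval.

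The synopsis hopes that the trial may give a signal of effectiveness, and fewer platelet transfusions is a listed key secondary outcome. If adjustment is considered only after the data are seen, it becomes a post hoc choice.

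**Working it through.** **Inputs from the documents.** Arm size: "Both arms will have a target enrollment of 10 activated subjects" (5.3). Accrual: "The expected enrollment is estimated to be 14 randomized subjects per year" and "The enrollment period will extend over 18 months" (5.3). Test level: "All statistical comparisons will be based on a two-sided model using a 0.05 level of significance and two-sided 95% confidence intervals" (11.5). Allocation is 1:1 in blocks of four.

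**Inputs the documents do not give, so assumed.** These are the share p of BMT patients and the BMT versus non-BMT difference D in mean transfusions, in within-group SDs. BMT patients are taken to arrive in random order.

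**The plan's own figure.** 14 per year × 1.5 years = 21, consistent with the target of 20. The target rests on feasibility; no effect size or SD is stated for transfusions. For scale, the difference detectable with 80% power at 10 per arm is (1.96 + 0.84) × √(2/10) = 1.25 SD (normal approximation).

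**Step 1: how often BMT is imbalanced.** With B BMT patients among 20, the number x in one arm of 10 is hypergeometric: P(x) = C(B,x)·C(20−B,10−x)/C(20,10), with C(20,10) = 184,756. The arms differ by |2x − B|.

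- B = 10, difference of 4 or more (x ≤ 3 or x ≥ 7): 2 × (1 + 100 + 2,025 + 14,400)/184,756 = 17.9%.
- B = 9, difference of 4 or more (which means 5 or more; x ≤ 2 or x ≥ 7): 2 × (11 + 495 + 5,940)/184,756 = 7.0%. Difference of 3 or more: 2 × (11 + 495 + 5,940 + 27,720)/184,756 = 37.0%.

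| BMT patients of 20 | Differ by ≥ 4 | Differ by ≥ 3 (odd counts) |
|---|---|---|
| 6 | 14.1% | |
| 7 | 5.7% | 35.0% |
| 8 | 17.0% | |
| 9 | 7.0% | 37.0% |
| 10 | 17.9% | |
| 11 | 7.0% | 37.0% |
| 12 | 17.0% | |

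With an odd BMT count the difference must be odd, so the two kinds of count have to be read separately.

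**Step 2: what an imbalance does.** With no drug effect, an imbalance of k BMT patients shifts the arm difference by (k/10) × D. A 7:3 split shifts it by 0.4 × D, which is 0.6 SD at D = 1.5.

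**Step 3: error rates.** 60,000 simulated trials per setting, blocks of four, p = 30% and 50%:

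| D | t-test type I error given imbalance ≥ 4 | Power for a 1-SD drug effect, t-test |
|---|---|---|
| 0.5 | about 7% | 54% |
| 1 | about 12% | 47-49% |
| 1.5 | about 18% | 39-41% |
| 2 | 24-25% | 32-34% |

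With adjustment, the conditional type I error is 4.6-5.4% and power is about 54% at every D. Averaged over all randomizations, the t-test's type I error is 4.9-5.1%, because low error in balanced trials offsets high error in imbalanced ones.

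**Step 4: precision.** Without adjustment, the outcome variance within an arm is 1 + p(1−p)D². With adjustment it is 1, multiplied by about 1 + 1/17 = 1.059 for estimating one covariate with 20 patients. The ratio of unadjusted to adjusted variance is therefore about [1 + p(1−p)D²]/1.059:

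| D | p = 20% | p = 50% |
|---|---|---|
| 0.5 | 1.04/1.059 = 0.98 | 1.0625/1.059 = 1.00 |
| 1 | 1.16/1.059 = 1.10 | 1.25/1.059 = 1.18 |
| 1.5 | 1.36/1.059 = 1.28 | 1.5625/1.059 = 1.48 |
| 2 | 1.64/1.059 = 1.55 | 2/1.059 = 1.89 |

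Simulation (15,000 runs per setting) agrees for D = 1, 1.5 and 2: 1.09, 1.28 and 1.56 at 20%; 1.18, 1.47 and 1.84 at 50%. At D = 0 the standard error grows by √1.059 = 1.03, or about 3%.

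**The case against.** The strongest reply is that the t-test is a valid test. Its error rate over all randomizations is 5%, and its interval already allows for chance imbalance. This stands. A reader might infer that the analysis is invalid or has an inflated false-positive rate, and the documents do not support that. What remains is a shift conditional on the imbalance that occurs, and lost precision.

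A reader might also take the missing stratification for the error. It is defensible with 20 patients, and the sentence in 11.2 speaks of disease group, which is not the same as BMT status. The gap is in 11.5.

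The size is assumed. The 6.2 values are ceilings. Clinicians may transfuse in anticipation of a low count, or for any reason they judge clinical, and patients whose threshold later rises stay on study. All of this may dilute D by an amount the documents do not show. At a 10% BMT share the simulated variance factors are only 1.03, 1.16 and 1.30 for D = 1, 1.5 and 2. This stands, and limits how firmly any gain can be claimed.

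Finally, the endpoint is secondary. It is tempting to call the transfusion difference a planning input for the larger trial, but section 11.7 refers to the trial's results in general and names only the recruitment rate. None of this is a reason to leave out a baseline covariate that is already collected and costs almost nothing.

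**Conclusion.** The point holds as a low-cost improvement to a secondary analysis. The protocol sets different triggers by BMT status, allocation does not balance it, and the planned comparison ignores it.

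With 6 to 12 BMT patients of 20, the arms differ by 4 or more in about 6-18% of trials: 14-18% for even BMT counts and 6-7% for odd counts, where a difference of 3 or more occurs in 35-37%. The 14-18% figure should not be read as applying to every count.

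Assuming a 20-50% BMT share, adjustment reduces the variance of the treatment estimate by factors of about 1.1-1.2 (D = 1), 1.3-1.5 (D = 1.5) and 1.5-1.9 (D = 2). At D = 0.5 it is neutral and at D = 0 slightly unfavourable. The existence of the gap rests on the text alone; its size rests on the assumed share and D. The primary endpoints are not affected.

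**What to change.** In section 11.5, replace the t-test for the number of platelet transfusions per patient with one pre-specified linear model containing arm and baseline BMT status (yes/no). Report the number of BMT patients in each arm, and mean transfusions by arm and BMT status.

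Use BMT status as known before the first dose, not the threshold later applied, because thresholds may change after activation. Keep the endpoint as section 11.1.2 defines it. A rate per day on drug would change the quantity estimated, because drug cessation happens after randomization. Naming a single model also avoids a choice of model after the data are seen.

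Randomization, sample size and data collection stay as they are. The cost is a short change to 11.5, one degree of freedom, and a standard error about 3% wider if BMT has no effect.

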11.3 Analysis Populations

Participants will be analyzed according to the groups to which they were initially randomized: tranexamic acid or placebo. All efficacy analysis will be by an Intent to Treat strategy. Participants will be included in the analysis if they received one or more dose of the study drug, even if participant discontinued participation, cross over between treatment groups or received prophylactic transfusions at a threshold higher than that prescribed in the protocol.

Efficacy analysis on patients will include data gathered on patients from the time of activation of the study drug until discharge or until a point 30 days following activation of the study drug, whichever time point occurs sooner. Any participants who have been consented to participate within the study and randomized to a treatment group but did not meet criteria to begin treatment with the study drug (whether due to development of

exclusion criteria or due to platelet count remaining >30,000/uL) and did not receive any doses of the study drug will not be included in the efficacy analysis.

The population of patients used for analysis of safety will be all patients who receive one or more dose of the study drug. Follow-up for mortality and for thrombotic events will occur at 7 days (+/- 3 days) and 30 days (+/- 3 days) post activation. Adverse events and Serious Adverse events will be based on clinical diagnosis obtained from review of the medical record and by patient report during the surveillance period. Patients will be assessed by daily visits and medical chart reviews by the investigator or study staff during the study period. Patients will be assessed by in-hospital visit (if in patient), clinic visit or telephone (if outpatient) during follow-up period after cessation of the study drug.

